10.7 Minority/Sex Analyses

In accordance with National Institutes of Health guidelines, modelling of the key outcomes will be completed to determine whether treatment response was significantly affected by participant minority/sex status using an interaction term between treatment arm and demographic factor being considered. The sex analyses will be completed for the infants. The minority analyses will be conducted for both the mother and infant outcomes.

10.8 Conceptual Model Analyses

Structural equation modeling¹⁸⁶ will be used to test the conceptual models described in **section 4.4**.

10.9 Health Economic Analytic Plan

A tertiary objective of MOMs is to conduct a health economic analysis comparing the costs and benefits of BUP-XR and BUP-SL; this section describes the analyses to be conducted.

10.9.1 Overview

The economic analyses will be conducted using well-established guidelines,^{132, 187, 188} from the perspective of the healthcare sector, as per the recommendation of the Second Panel on Cost Effectiveness in Health and Medicine.¹³² The healthcare sector perspective includes all formal (medical) costs incurred by the system on behalf of participants in each arm, and their infants. First, we will determine and value the resources required to start up and manage each treatment strategy on a continuing basis, by site. Next, we will evaluate whether BUP-XR for OUD treatment of pregnant women is associated with more primary, obstetrical, and behavioral healthcare services but fewer emergency and inpatient services; enhanced participant wellbeing; and economic viability, compared to BUP-SL.

The data sources defined in **section 7.5** will be used to capture all available healthcare service utilization for participants in both arms over the entire study period (i.e., pregnancy-delivery and postpartum). The resource costing method will be used to estimate participant-level costs. This method is a powerful tool in a clinical trial environment; it involves determining a price weight for each resource unit consumed and multiplying price weights by units of service.^{132, 188, 189} Unit costs will be derived from sources reflecting national real-world costs faced by the healthcare sector.

The U.S. Department of Veterans Affairs Federal Supply Schedule will be used to value all medications, as per the current guidelines.¹³² Medicare fee-for-service payments will be used to value other healthcare resources, as these payments are designed to reimburse providers for the resources that would be used to treat a typical patient with a given condition and are adjusted for relevant factors that are unique to the patient or provider,¹⁹⁰ as opposed to also including a component for profit and risk adjustment.¹³²

To begin, we will conduct bivariate analyses (t-tests for continuous measures and chi-square tests for categorical measures; nonparametric tests will be used for measures that fail to satisfy the assumptions of parametric tests) to test for baseline differences between arms for factors relevant to the economic analysis that may not have been considered in the randomization process (e.g., HRQoL). All data will be analyzed under an intent-to-treat principle. We will model the person period monthly during the pregnancy and delivery phase, and every other month during the 12-month postpartum phase. All analyses will be conducted using a multivariable Generalized Linear Mixed Model (GLMM). The GLMM is an extension of the GLM that allows for the inclusion of random effects. The multivariable aspect of the model is crucial as it allows for the control of factors that are unbalanced between arms because they were not accounted for in the randomization process or may have become unbalanced due to loss to follow-up. The GLMM allows one to choose the most appropriate mean and variance functions according to the fit of the data, and uses all available data for each participant, regardless of whether or not it is complete, making it an ideal statistical procedure for intent-to-treat approaches.¹⁸⁸ Given the differences in mechanisms to generate data, separate multivariable GLMMs will be estimated to predict the mean value for each resource and outcome, at each time period, by study arm. The statistical method of recycled predictions will be used to obtain the final predicted mean values, which will be summed and tested over the pregnancy and delivery phase, and over the entire study period.¹⁸⁸ To account for sampling uncertainty in point estimates, the p-values and standard errors will be estimated using nonparametric bootstrapping techniques within the multivariable framework. All monetary values will be adjusted for inflation. Follow-up measurements obtained beyond 12 months of baseline will be discounted for time preference using the recommended rate of 3%.^{132, 188} Our team has extensive experience applying these methods.¹³⁸⁻¹⁴¹

10.9.2 Intervention Costs

The resources used to implement and administer each treatment strategy, by site, will be estimated using a combination of macro- and micro-costing analyses. To the extent possible, costs will be estimated using a macro-costing (“top down”) approach based on information obtained from the PAASA (see **section 7.4**). These data may be supplemented with data collected during semi-structured interviews with site clinical leaders, that will allow us to assign individual resources (time and materials) used to deliver the intervention using micro-costing (“bottom up”) techniques.

10.9.3 Healthcare Service Utilization

The analytic methods described in **section 10.9.1** will be used to test for differences in utilization of healthcare services, as well as their associated costs, at baseline and over time.

10.9.4 QALYs

We will test for differences in QALYs gained between study arms over the pregnancy and delivery phase, and over the entire study period. A multivariable GLMM regression will be used to estimate the predicted health utility index value for each arm at each time period. The predicted health utility index value will be used to weight the amount of time associated with the arm’s typical health

state, and mean QALYs gained over time for each arm will be estimated using the area under the curve methodology.^{132, 188, 191}

10.9.5 ICERs and Cost-Effectiveness

The costs calculated in **sections 10.9.2** and **10.9.3** will be combined and the difference between the two arms will be calculated to form the numerator of the ICER (see **section 7.5**). Four ICERs will be calculated, since we are evaluating two measures of effectiveness (QALYs; Abstinent Years) over two time periods of interest (pregnancy and delivery; entire study period). ICER confidence intervals will be estimated using nonparametric bootstrapping techniques within the multivariable framework. Parametric methods based on parameters obtained from bootstrapping will be used to estimate acceptability curves, which will illustrate the probability that the BUP-XR is a good value relative to BUP-SL for different willingness-to-pay thresholds (i.e., cost-per-QALY and cost-per-Abstinent-Year). ICERs will be calculated and acceptability curves will be constructed regardless of the statistical significance for individual cost and effectiveness differences, as the power to detect a difference in costs and effects jointly exceeds the power to do so individually.¹⁸⁸

10.9.6 Missing Health Economic Data

To help address censored data we will model the monthly person period and estimate all multivariable regressions using the GLMM, which uses all available data for each participant, regardless of whether the data are complete.¹⁸⁸ In all cases we will diagnose the mechanism of censoring or missingness (i.e., missing completely at random (MCAR), missing at random (MAR), or missing not at random (MNAR)). Logistic regression models predicting missingness, based on participant characteristics and prior measures, will be used to determine whether the data are MCAR and thus ignorable.¹⁹² If not, we will address the missingness using the most appropriate method.¹⁸⁸ We will also conduct extensive sensitivity analyses, including MNAR approaches, to examine the robustness of our outcomes under varying assumptions.¹⁹³

10.9.7 Sensitivity Analyses

Sensitivity analyses will be performed to account for uncertain precision in assumptions and parameter estimates applied in the analyses.¹³² For example, we will test the robustness of the results as they pertain to variations in the unit cost estimates, and in the cost of implementing and managing each treatment strategy. Also, values estimated using the more robust and efficient GLMM regression will be compared to those estimated using the more transparent ordinary least squares regression, as well as to the unadjusted mean values.

10.10 Neurodevelopmental Outcomes Analysis

A quaternary objective is to evaluate the impact of BUP-XR, relative to BUP-SL, on neurodevelopment when the infant/child is approximately 12 and 24 months of age. The main outcome is the score on the cognitive subscale of the Bayley™-4 at 24 months of age. The primary method of analysis will be a t-test. For modelling purposes, a mixed model may be used to account for the repeated measures nature of the data and potential covariates, or an alternative approach that allows for multiple outcome measures per infant/child and construction of a contrast to test the treatment effect at 24 months of age.

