7.9 Infant Neurodevelopmental Outcomes of the Quaternary Objective

Infant caregivers will be offered the opportunity to participate in the infant neurodevelopmental outcomes (INO) sub-study (see **section 8.10**). Individuals signing consent will participate in the assessments listed below. In addition, a locator form (see **section 7.7**) will be completed at the 12-month assessment to facilitate retention at the 24-month assessment.

Demographics. The demographics questions from the PhenX toolkit will be utilized.

BayleyTM-4. The BayleyTM-4¹⁰² is considered the gold standard assessment of early child development and includes cognitive, language, fine motor, and gross motor subscales. The BayleyTM-4 will be used to evaluate infants at the 12- and 24-month assessments by a certified examiner who is blind to the CTN-0080 participant's treatment arm. The main outcome is the score on the cognitive subscale at the 24-month assessment. While some sites may be equipped to perform this assessment in-clinic, it is likely that this assessment may occur at other clinical sites either within the institution or at an external clinical site providing these services. As determined by the provider, it is permissible for this assessment to be administered as a home visit.

Child Behavior Checklist (CBCL). The CBCL¹⁷⁴ is completed by caregivers and includes items that describe behavioral, emotional, and social problems that characterize preschool children. The CBCL is the measure used by the National Institute of Child Health and Human Development Neonatal Research Network to assess problem behaviors at the 22-26-month visit and will be collected at the 24-month assessment in the INO. Flexibility in the collection of this assessment is allowed including collection via mail.

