8.4 Randomization Plan

Eligible participants will be randomized in a 1:1 ratio to BUP-XR or BUP-SL. The randomization process will be performed by computer by the Data and Statistics Center (DSC). A permuted block randomization procedure with random block sizes will be implemented to balance on site, whether participants are on BUP-SL at the time of randomization (yes vs. no), and EGA at time of randomization (6 weeks - 18 weeks vs. 19 weeks - 30 weeks); EGA was used as a stratification variable in the MOTHER trial.⁴³

Table 3: Overview of Assessments and Procedures																			
Perinatal Phase:	Pregnancy					Delivery & Immediate Post-partum	Post-partum												As Needed
	Pre- Screen	Screen/ Base ¹	Random- ization ²	Week 3	Monthly Post-rand ³		Month 1	Month 2	Month 3	Month 4	Month 5	Month 6	Month 7	Month 8	Month 9	Month 10	Month 11	Month 12	
Research Visits		X	X	X	X		X		X			X			X			X*	
Screening Assessments																			
Pre-screen verbal consent	X																		
Pre-screen interview	X																		
Informed Consent		X																	
Medical record releases		X																	X
Demographics/PhenX Tier 1		X																	
DSM-5 checklist		X																	
PRISM-Suicide/Homicide		X																	
Blood Chemistry ^{4,5}		X																	
Urine Pregnancy Test		X																	
Estimated Gestational Age ^{4,5}		X																	
Treatment and Research Status		X																	
Medical and Psych History (Hx)		X																	
Drop-out Risk Assessment		X																	
Weekly Medication Check Visits ⁶																			
BUP-XR administration/documentation			Weekly administration ⁶				Weekly or Monthly administration ⁷												
BUP-SL dispense/document; adherence			Weekly - Monthly dispensing ⁸				Weekly - Monthly dispensing ⁸												
Adverse Events/Serious Adverse Events			Weekly ⁶				Weekly ⁶												
Injection Site Reaction Reporting Form																			X
Urine drug screen		X	Weekly ⁶				Weekly ⁶												
Infant sedation assessment							Weekly ⁶												
Pregnancy Test (BUP-XR)							Monthly for participants on monthly BUP-XR formulation												X
Medication Check Visit Compensation			\$20 per visit not corresponding to a research visit																
Table 3 continued on next page																			

Table 3 continued on next page

Table 3: Overview of Assessments and Procedures																			
Perinatal Phase:	Pregnancy					Delivery & Immediate Post-partum	Post-partum												As Needed

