
10.3.2 Key Outcomes

Illicit opioid abstinence during pregnancy. As noted previously, this primary outcome measure is based on urine testing. It is operationalized as the percent of expected UDSs that are negative for illicit opioids. One UDS is expected at the time of each weekly Medication Check Visit between randomization and delivery – any missing UDS is imputed as positive (see **section 10.3.5**). The number of expected UDSs will be dependent on the length of time between randomization and

delivery, thus we operationalize this primary outcome measure as the *percent* of expected UDSs that are illicit opioid-negative.

The non-inferiority design results in the following hypotheses where μ_A is the mean in arm A and Δ the non-inferiority margin:

$$H_0(BUP - XR \text{ is inferior to BUP - SL}): \mu_{XR} - \mu_{SL} \leq -\Delta$$

$$H_1(BUP - XR \text{ is non - inferior to BUP - SL}): \mu_{XR} - \mu_{SL} > -\Delta .$$

To evaluate non-inferiority at the 2.5% significance level, the two-sided 95% confidence interval for the treatment effect, $\mu_{XR} - \mu_{SL}$, will be calculated using a mixed effects model where treatment arm is a fixed effect and the three randomization factors (site, EGA and BUP-SL status at randomization) are random effects. If the lower limit of the confidence interval is greater than -0.15 (i.e., $\Delta=0.15$), we will reject the null hypothesis and conclude non-inferiority of BUP-XR to BUP-SL. Only if the null hypothesis is rejected will superiority of BUP-XR to BUP-SL be considered. This will involve examining the two-sided 95% confidence interval for the treatment effect, $\mu_{XR} - \mu_{SL}$. If the lower limit is above zero, then we can conclude that the extended-release formulation is superior to the sublingual formulation. If this order of testing is followed, then there is no need to adjust for multiplicity.^{176, 181} Additional covariates for secondary modeling are described in **section 7.4**. In the event that the distributional assumptions involved in the mixed effects model are not met, which is likely, alternative non-parametric methods will be considered for this modelling such as quantile regression.

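### The primary analysis of the 24-month Bayley-4 cognitive score omits the three randomization factors, which costs precision if those factors predict the score

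*Combined protocol and SAP*

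**What the plan says.** Section 10.10 (Neurodevelopmental Outcomes Analysis) defines the outcome and the test: "The main outcome is the score on the cognitive subscale of the Bayley™-4 at 24 months of age" and "The primary method of analysis will be a t-test". No covariate or stratum is attached to the test. The section then allows an alternative for modelling purposes, in which "a mixed model may be used to account for the repeated measures nature of the data and potential covariates". That model is optional, does not replace the t-test, and does not say which covariates it would hold.

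Section 8.4 (Randomization Plan) describes the stratification: "A permuted block randomization procedure with random block sizes will be implemented to balance on site", continuing with "whether participants are on BUP-SL at the time of randomization (yes vs. no), and EGA at time of randomization" in two bands, 6–18 and 19–30 weeks. For the maternal primary outcome, section 10.3.2 fits a mixed model in which "the three randomization factors (site, EGA and BUP-SL status at randomization) are random effects". Section 10.4.2 adds that power must be sufficient with these factors in the model even when they are unrelated to the outcome.

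Two further places bear on the point. Section 4.6 presents the neurodevelopment work as a chance to evaluate the data with control for prospectively collected contributing factors. Section 7.4 says that study site will be a covariate in secondary analyses.

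**The concern.** Stratified randomization makes the arms similar on the stratification factors. A two-sample t-test does not use that. Any variance in the score explained by site, gestational-age stratum or BUP-SL status stays in its residual error, even though balance has largely removed it from the true sampling variability of the difference. When the factors matter, the standard error is therefore too large for the design.

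Interval width is what counts here, because section 5.4 predicts no difference between the arms. A null result is informative only as far as its interval excludes differences of concern.

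There is a second reason to adjust. Under section 8.10.2, caregivers are typically recruited to the sub-study postpartum, long after randomization, and only those who consent are assessed. Balance within strata may be partly lost among the children tested. Adjustment corrects imbalance on these three factors; the t-test does not.

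**Working it through.** **Inputs from the plan.** Randomization is 1:1 ("Eligible participants will be randomized in a 1:1 ratio to BUP-XR or BUP-SL", section 8.4). About 200 women are to be randomized at about 10 sites (sections 3.3 and 6.2). The stratifiers are site, gestational age (two levels) and BUP-SL status (two levels), giving 10 × 2 × 2 = 40 strata.

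**Not in the plan.** For the Bayley-4 score there is no standard deviation, sample size, target difference, or share of variance explained by the factors (R²). All values below for R², follow-up, block sizes and stratum prevalences are assumptions.

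**The plan's own figure.** The only power figure is Table 8, for the urine-screen outcome. With variance 0.11 (SD 0.3317), margin 0.15 and one-sided 2.5%:

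- N = 176: 0.15 / (0.3317 × √(2/88)) = 3.00, and Φ(3.00 − 1.96) = 85.1% (stated 84.9%).
- N = 200: 0.15 / (0.3317 × √(2/100)) = 3.20, and Φ(3.20 − 1.96) = 89.2% (stated 89.0%).

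Table 8 is reproduced, but it says nothing about the size or precision of the Bayley-4 analysis.

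**Interval half-widths by formula, in SD units, equal arms.**

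- t-test: t(0.975, N − 2) × √(4/N).
- Adjusted: t(0.975, N − 13) × √(4(1 − R²)/N). The 13 parameters are arm, 10 sites, gestational-age stratum and BUP-SL status.

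Example with N = 100 and R² = 0.20: 1.984 × 0.200 = 0.397 against 1.988 × √0.032 = 0.356, a ratio of 1.116.

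**Simulation check.** There were 4,000 runs per setting, with 200 randomized in permuted blocks of 2 or 4 within the 40 strata. Site carried 60% of R² and the other two factors shared the rest equally. Either all 200 or a random 55% (about 110) were followed. Site was fitted as fixed indicators. The Monte Carlo error of a 95% coverage figure is √(0.95 × 0.05/4000) = 0.3 points.

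Ratio of t-test interval width to adjusted width, and t-test coverage:

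| Assumed R² | Formula, N = 80 to 200 | Simulated, all followed | Simulated, 55% followed | t-test coverage, all / 55% |
|---|---|---|---|---|
| 0 | 0.997–1.000 | 0.995 | 0.970 | 95.0% / 94.9% |
| 0.05 | 1.023–1.026 | 1.021 | 0.995 | 95.7% / 95.2% |
| 0.10 | 1.051–1.054 | 1.050 | 1.023 | 96.1% / 95.4% |
| 0.20 | 1.115–1.118 | 1.113 | 1.084 | 96.7% / 95.5% |
| 0.30 | 1.192–1.195 | 1.191 | 1.160 | 97.6% / 96.2% |

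Coverage of the adjusted interval stayed between 94.4% and 95.5%. The formula assumes that balance is intact. The 55% column is lower because random loss disturbs balance within strata and because the 13 parameters weigh more in a smaller sample.

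**The case against.** The strongest reply is that nothing is broken. The t-test kept its coverage at or above nominal, within simulation error, in every setting, so a reader who infers that it is invalid goes further than the plan supports. The only cost is possible precision, and that cost is zero if the factors do not predict the score. With partial follow-up and an R² of 0.05 or less, the t-test interval is no wider than the adjusted one, and may be slightly narrower. This stands, and it is why the gain has to be stated as conditional.

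A reader might also infer that Bayley-4 examiners differ by site. Section 7.9 does not say so. It requires a certified examiner blind to arm, and of venue it says that "it is likely that this assessment may occur at other clinical sites either within the institution or at an external clinical site". Home visits are also allowed, so venue may vary within a site as well as between sites. A site effect on scores is plausible with about 10 sites, but it is not documented.

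Nor can the gain be expressed as power. The plan sets no target difference or power for this sub-study, and section 5.4 expects no difference.

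The comparison with the rest of the plan has limits too. Section 10.3.2 expects the assumptions of the primary model to fail and mentions quantile regression. Section 10.3.3 allows unadjusted tests for some secondary outcomes. Section 7.4 does not say whether its statement on site reaches the quaternary objective. Section 4.6, however, concerns the neurodevelopment data directly, and a primary t-test does not deliver the control described there. The optional mixed model does not close the gap, because it is neither primary nor specified.

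**Conclusion.** The point holds as an inexpensive improvement. The primary analysis in section 10.10 omits all three stratification factors. This is out of step with the maternal primary model, with the intent stated in section 4.6, and with the general statement on site in section 7.4.

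The possible loss is in precision. It is about 0 to 19% in interval width with full follow-up as R² goes from 0 to 0.30. With 55% follow-up, the t-test interval is about 3% narrower at R² = 0, 2% wider at 0.10, 8% wider at 0.20 and 16% wider at 0.30. These figures rest on assumed R², follow-up and block sizes, so the documents do not establish that the interval will in fact be too wide.

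It would also be too strong to read adjustment as a remedy for selective enrolment. It corrects imbalance on these three baseline factors. It does not correct selection through events after randomization, such as a change of custody or a caregiver's decision not to consent.

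**What to change.** In section 10.10, and in the standalone statistical analysis plan mentioned in section 10.4.2, name as primary a linear model of the 24-month cognitive score on arm, site (random effect), gestational-age stratum and BUP-SL status at randomization. Report the adjusted difference between arms with its 95% confidence interval, and keep the t-test as a supportive analysis.

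The change is to wording only. All three factors are fixed before treatment and are already in the randomization record, so adjusting for them introduces no post-randomization bias. The cost is a few degrees of freedom and a slight loss of precision if the factors are unrelated to the score: about 3% in width in the 55% follow-up simulation, where site was fitted as fixed effects. A random site effect should cost no more than that, but it was not simulated.

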8.10.3 INO Visits

At the initial study visit, when the infant is approximately 12 months of age, interested caregivers will complete the informed consent process, provide demographic information, including information about socioeconomic status, and will provide locator information to aid retention efforts for the 24-month assessment. The Bayley™-4 will be administered at both visits. While some sites may be equipped to perform the Bayley in-clinic, it is likely that this assessment may occur at other clinical sites either within the institution or at an external clinical site providing these services. As determined by the provider, it is permissible for this assessment to be administered as a home visit.

In addition, at the 24-month assessment, the CBCL will be administered to the caregiver. Flexibility in the collection of the CBCL is allowed, including collection via mail.

If the caregiver changes between the 12-month and 24-month time period, demographic information will be collected a second time.

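### The primary t-test of the 24-month Bayley-4 cognitive score leaves out children lost after 12 months and ignores their 12-month scores, which costs precision and can bias the arm comparison if loss differs by arm

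*Combined protocol and SAP*

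**What the plan says.** Section 10.10 defines the endpoint: "The main outcome is the score on the cognitive subscale of the Bayley™-4 at 24 months of age". It then states: "The primary method of analysis will be a t-test". A repeated-measures approach appears only as an option: "a mixed model may be used to account for the repeated measures nature of the data and potential covariates", or an alternative that yields a treatment contrast at 24 months.

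The 12-month score is collected by design. Section 7.9 says the Bayley-4 "will be used to evaluate infants at the 12- and 24-month assessments by a certified examiner", and section 8.10.3 says "The Bayley™-4 will be administered at both visits". Caregivers consent at the 12-month visit, so a child who enters then is assessed before any loss to the 24-month visit can occur.

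Loss between the visits is foreseen. Caregivers "will provide locator information to aid retention efforts for the 24-month assessment" (section 8.10.3), and section 7.9 makes the same provision. No expected loss rate is given.

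The missing-data rules lie elsewhere. Section 10.3.5 covers the urine screens and infant opioid-treatment days, and section 10.9.6 covers the health economic data. Neither mentions the Bayley-4. Section 10.4.2 refers to a standalone SAP whose text is not included here.

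**The concern.** A two-sample t-test of 24-month scores, with no imputation rule, can be computed only on children who have that score. The protocol does not call this a complete-case analysis, but it is one. A child tested at 12 months and lost by 24 contributes nothing, although a score on the same scale is in hand.

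Two things are at stake. The first is precision, in a sub-study of unstated size drawn from a trial of about 200 women. The second is bias. The trial is open-label and hypothesizes better maternal adherence and less drug use on BUP-XR. If those effects occur, family stability, and with it follow-up, could differ between arms. The documents give no figures on this, so it is a possibility and not a finding. Section 5.4 predicts no difference between arms, so an attrition artefact of a few points would bear directly on the stated conclusion.

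**Working it through.** The plan gives no sample size, SD, power or loss rate for this analysis, so it has no figure to reproduce.

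**Assumptions (none from the documents).** The 12- and 24-month scores are bivariate normal with SD 15 and correlation r = 0.5 or 0.7. The comparison is the t-test on 24-month completers against the likelihood estimate using both visits, which is the 24-month contrast of an unstructured mixed model. Differences are BUP-XR minus BUP-SL.

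**1. Precision under random loss.** With a fraction m lost, the variance of the likelihood estimate relative to the t-test is approximately 1 − m·r². For m = 0.30:
- r = 0.5: 1 − 0.30 × 0.25 = 0.925; SE ratio √0.925 = 0.962. The t-test SE is 1/0.962 = 1.04 times as large.
- r = 0.7: 1 − 0.30 × 0.49 = 0.853; SE ratio √0.853 = 0.924. The t-test SE is 1/0.924 = 1.08 times as large.

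Simulation with 80 per arm gives SDs of 2.80 v 2.69 (r = 0.5) and 2.83 v 2.63 (r = 0.7).

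**2. Bias when loss depends on the 12-month score.** Suppose 50% are lost below the 12-month median and 10% above it, so 30% are lost overall. A half-normal has mean 0.798 SD, so the returners' mean 12-month score is shifted by 0.798 × (0.5 × 0.9 − 0.5 × 0.5)/0.70 = 0.228 SD. The shift carried to the 24-month mean is 15 × r × 0.228 = 3.42r points.
- *Same pattern in both arms, no effect:* 3.42r − 3.42r = 0.
- *BUP-SL 50%/10%, BUP-XR 40%/20%:* the BUP-XR shift is 0.798 × (0.5 × 0.8 − 0.5 × 0.6)/0.70 = 0.114 SD, or 1.71r points. The bias is −1.71r = −0.9 (r = 0.5) to −1.2 (r = 0.7).
- *BUP-SL 50%/10%, BUP-XR 30% at random:* the bias is −3.42r = −1.7 to −2.4. In 6,000 simulated trials of 60 per arm it was −1.6 to −2.4, with 8.1% to 11.5% rejection at a nominal 5%.

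**3. A second loss model.** Here the log-odds of being seen at 24 months rise by 0.8 per SD of the 12-month score. Bias comes from 1,000,000 children per arm and rejection from 4,000 trials of 80 per arm. Each range runs over r = 0.5 and 0.7.

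| Loss pattern, no true effect | t-test bias (points) | t-test rejection |
|---|---|---|
| Same dependence, same rate | 0 | 4.6–5.1% |
| Same dependence, loss 32% v 22% | −0.6 to −0.7 | 4.9–5.7% |
| Score-related in BUP-SL only | −1.7 to −2.4 | 8.7–13.2% |
| Opposite directions by arm (extreme) | −3.5 to −4.8 | 20.7–40.5% |

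The likelihood estimate is within 0.04 points of the truth in every row.

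**4. Where the model does not rescue the comparison.** Apply the 50%/10% v 30% pattern to the 24-month score itself. The t-test bias is about −3.4, and the model's is −2.6 (r = 0.5) or −1.8 (r = 0.7). If loss depends on change that the 12-month score does not predict, the two are equally biased: about −2.9 (r = 0.5) and −2.4 (r = 0.7).

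**The case against.** A reader might infer that any loss related to early development biases the comparison. It does not. The second step and the first row of the table show zero bias and nominal error when the dependence is the same in both arms and there is no effect, which is what section 5.4 predicts. The documents contain no evidence that loss will differ by arm.

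A reader might also infer that the mixed model cures attrition. It corrects only for loss that depends on observed scores. If instability arises after 12 months and drives both loss and poorer development, the model is biased too. It also cannot help children who never enter at 12 months.

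The design reduces loss as well. Whoever is the caregiver can take part, a change of caregiver is provided for, and home or external-site testing is allowed. The model is already named in 10.10, the unseen SAP may contain a rule, and this is the quaternary objective of an optional sub-study.

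All of this stands and limits the size of the point. It does not justify setting collected scores aside in the primary test. For the economic data, section 10.9.1 chooses a mixed model that uses all available data, and section 10.9.6 commits to sensitivity analyses for data missing not at random. The child outcome has neither commitment.

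**Conclusion.** The point holds in a conditional form. The precision loss needs no differential attrition: the t-test SE is about 4% to 8% larger with 30% random loss and a correlation of 0.5 to 0.7. Bias needs a difference between arms. It is 0.6 to 0.7 points if only the loss rate differs (32% v 22%), with error close to nominal. It is about 1.6 to 2.4 points, with 8% to 13% false rejection, if loss is score-related in one arm only. These sizes rest on the assumed SD of 15, the correlations and the loss patterns. The documents supply none of them, and the one-arm pattern is an adverse case. The change is worth making because a better method is already named and its data are already collected, but it does not threaten the trial's main conclusions.

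**What to change.** In section 10.10:

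- Make the primary analysis a repeated-measures mixed model of the 12- and 24-month Bayley-4 cognitive scores, with arm, visit and arm-by-visit terms and unstructured covariance. Include every child with at least one score.
- Report the 24-month arm contrast with its 95% confidence interval.
- Keep the 24-month t-test as a supportive analysis of completers.
- State the missing-data assumption, and add a sensitivity analysis for data missing not at random, in line with section 10.9.6.
- Report by arm how many children enter at 12 months and how many return, because no analysis of the two visits recovers children never enrolled.

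The cost is wording in the analysis plan and a slightly less simple analysis. No new data are needed.
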